3.1. Overall Design

The design of the study is as follows:

- Comparative: 2 groups. 100 participants per group
- Interim statistical analysis: planned after 50 patients
- Random: the randomization is controlled by APACHE score
- Multi-site: Israel, United States, Europe

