7.1. Participant Discontinuation/Withdrawal from The Study

Each subject (or delegate) will be informed of his/her right to withdraw from the study at any time and for any reason. The Investigator may withdraw a subject from the study at any time if he considers that remaining in the study compromises the subject's health.

Additional criteria for discontinuation/withdrawal:

- The insertion of the feeding tube has failed after 3 attempts in each nostril
- Disease progression which requires discontinuation of the study intervention
- If the participant meets an exclusion criterion (either newly developed or not previously recognized) that precludes further study participation.

In the event a subject discontinuation/withdraws from the study the following procedures will be observed:

- The reasons for any subject discontinuation/withdrawal will be recorded on the study completion form of the eCRF.
- The investigator will inform the sponsor of the subject's early withdrawal for any reason.
- If withdrawal is caused by an adverse event that the investigator considers may be related to the device, it will be reported to the IRB and to the Sponsor.

Subjects who signed the informed consent form and are randomized but do not receive the study intervention are considered screen failures and may be replaced. Subjects who sign the informed consent form, and are randomized and receive the study intervention, and subsequently withdraw, or are withdrawn or discontinued from the study may also be replaced.

 ART MEDICAL PATIENT SAFETY TECHNOLOGY	Number: CRO-C-2822	Date issued: 01-Mar-2021
	Rev.06	Page 25 of 35

Subject: smART Plus Comparative Study Protocol - Beilinson

In addition, this study may be temporarily suspended or prematurely terminated if there is sufficient reasonable cause.

Circumstances that may warrant termination or suspension include according to the PI decision, but are not limited to:

- Determination of unexpected, significant, or unacceptable risk to participants
- Demonstration of efficacy that would warrant stopping
- Insufficient compliance to protocol requirements
- Data that are not sufficiently complete and/or evaluable
- Determination that the primary endpoint has been met
- Determination of futility

Study may resume once concerns about safety, protocol compliance, and data quality are addressed, and satisfy the sponsor, IRB and/or Food and Drug Administration (FDA).

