9.1 Sample size consideration

Approximately 200 subjects will be enrolled for the complete multi-center comparative study (100 per group). An interim analysis will be performed after 100 subjects (50 in each group) are enrolled on the primary endpoint.

1- Based on the primary endpoint at interim analysis (feeding efficiency):

Sample size rationale:

The rationale for sample size calculation is based on a difference in feeding efficiency between the tested group (with smART+ System) and the current standard practice (group B).

Sample size justification:

The comparison between groups of food consumption estimations is reflected by Effect size, calculated as the difference between the groups normalized by the common standard deviation.

The calculation uses the following formulation: (Estimation in the tested group - Estimation in control group)/Common standard deviation Error! Bookmark not defined.Error! Bookmark not defined.

A sample size of 50 in each group will have 90% power to detect an **effect size of 0.70** using a two-group t-test with a 0.025 two-sided significance level. [1, 2]

A significance of 0.025 was used instead of the usual 0.05 (alpha adjustment) due to the increase in the chance of making a Type 1 error following two subsequent analysis.

2- Based on the secondary endpoints at end of study:

2.1 Ventilation days:

Sample size rationale:

Subject: smART Plus Comparative Study Protocol - Beilinson

The rationale for sample size calculation is based on a difference in Ventilation days between the tested group (with smART+ System) and the current standard practice (group B).

Sample size justification:

The comparison between groups in ventilation days is reflected by Effect size.

A sample size of 100 in each group will have 90% power to detect an **effect size of 0.46** using a two group t-test with a 0.05 two-sided significance level. [1, 2]

2.2 Ventilation Associated Events:
Sample size rationale:

The rationale for sample size calculation is based on a difference in the proportion of subjects with Ventilation-Associated Events between the tested group (with smART+ System) and the current standard practice (group B) of 20%.

Sample size justification:

A two group continuity corrected c^2 test with a 0.05 two-sided significance level will have 90% power to detect the difference between a Group 1 proportion, p_1 , and a Group 2 proportion, p_2 (**odds ratio of 2.70**) when the sample size in each group is 100.[3]

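### Section 7.1 allows an efficacy stop by PI decision that is not tied to the planned interim or its 0.025 level, and section 9.1 does not say whether a positive interim ends enrolment

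*Combined protocol and SAP*

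**What the plan says.** Section 7.1 gives reasons for suspending or ending the whole study, introduced by "Circumstances that may warrant termination or suspension include according to the PI decision, but are not limited to". Two of them concern efficacy: "Demonstration of efficacy that would warrant stopping" and "Determination that the primary endpoint has been met". Neither is linked to an analysis time, a boundary or a significance level.

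Section 9.1 contains the alpha plan: "An interim analysis will be performed after 100 subjects (50 in each group) are enrolled on the primary endpoint". The primary endpoint (feeding efficiency) is sized there at 50 per group, effect size 0.70, two-sided 0.025, 90% power. The reduced level is explained by there being two analyses. The section does not say what happens to enrolment if the interim is positive. The 100-per-group figure is supported by a second block, headed "Based on the secondary endpoints at end of study", which covers ventilation days, ventilator-associated events (VAE) and ICU length of stay.

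Two other places bear on this. Section 9.2.1 treats p values of 5% or less as significant for every test, with no exception for the primary endpoint. Section 3.1 reads "Interim statistical analysis: planned after 50 patients", which disagrees with section 9.1 unless it means 50 per group.

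**The concern.** The primary endpoint is powered to succeed at the halfway point, the second hundred patients are justified by the secondaries, and section 7.1 makes success on the primary a permitted reason to end the trial. Nothing reconciles these three statements.

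Two things are at stake, in different scenarios. First, the 0.025 level protects the primary only if efficacy is judged at the two planned analyses and at that level. Section 7.1 imposes neither limit, section 9.2.1 points to 5%, and section 5.1 makes the trial open-label. Second, even a stop that fully respects the alpha plan leaves the secondaries with half the sample on which their stated power rests.

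**Working it through.** **Inputs.** From section 9.1: primary effect size 0.70, 50 per group, two-sided 0.025; ventilation days and length of stay effect size 0.46, 100 per group, two-sided 0.05; VAE odds ratio 2.70, 100 per group, continuity-corrected test, with a 20% that can be read as the control rate or as the difference. From section 9.2.1: 5% for all tests. From section 5.1: 1:1 allocation. No dropout is applied, because none is stated and section 7.1 allows replacement.

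**Formula for means.** Two-sample t-test with noncentrality d·√(n/2) and 2n − 2 degrees of freedom, n per group.

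**The plan's own figures**
- Primary: 0.70·√25 = 3.50, 98 df, critical t 2.276. Power 88.8% (normal approximation 89.6%), against 90% stated.
- Ventilation days and length of stay: 0.46·√50 = 3.253, 198 df, critical t 1.972. Power 89.9%. The stated 90% reproduces.

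**Power after a stop at 50 per group**
- Ventilation days and length of stay: 0.46·√25 = 2.30, 98 df, critical t 1.984. Power 62.5%. Keeping 90% would need an effect size of about 0.65.
- VAE at an assumed 20% versus 40%, Fleiss continuity correction: the effective n is 90.25 for 100 per group and 40.5 for 50 per group. Power is Φ[(0.20·√n − 1.96·√(2·0.3·0.7)) / √(0.16 + 0.24)], that is Φ(0.996) = 84.0% at 100 per group and Φ(0.004) = 50.2% at 50 per group.

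**Range for VAE at odds ratio 2.70**

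| Reading | 100 per group | 50 per group |
|---|---|---|
| Control 20%, other arm 40.3% | 85.1% | 51.4% |
| Difference of 20 points (19.4% vs 39.4%) | 84.4% | 50.6% |
| Control 20%, other arm 8.5% | 56.8% | 27.3% |
| Lower-arm rate 30% to 50% | 90% to 92% | 58% to 61% |

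The stated 90% does not reproduce on any reading that uses the 20%. That is a separate matter, not caused by section 7.1.

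**Chance that the condition is available at the interim.** If d = 0.70 is true, the primary crosses 0.025 at 50 per group with probability 88.8%. If section 3.1 means 50 patients in total (25 per group), that chance is 56.7%, and power for d = 0.46 after a stop there is 35.7%.

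**Overall type I error for the primary.** For two looks at half and full information this is 1 − P(|Z₁| < c, |Z₂| < c), with correlation √0.5 = 0.707. The four-look figures come from simulation with equally spaced looks. Four looks is an assumption; the documents give no such number.

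| Looks | each at 0.025 | each at 0.05 |
|---|---|---|
| 2 (planned) | 4.3% | 8.3% |
| 4 (assumed) | 6.7% | 12.6% |

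**The case against.** The strongest defence is that section 7.1 is permissive. It lists circumstances that may warrant a stop, requires reasonable cause, and refers only to efficacy sufficient to justify stopping. Section 9.1 plans about 200 subjects and places the secondaries at the end of the study, which points to continuing past the interim. A stop at the planned interim at 0.025 is also inside the alpha plan, at 4.3% overall. Lower secondary power after an efficacy stop is an ordinary cost of having an interim, not an error in itself. Finally, repeated comparative looks may be hard in practice: section 5.2.8 has the sponsor extract the console data, and section 5.3.1 leaves discarded control feed to later video analysis.

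Much of this stands, and it rules out some stronger readings. A reader might infer that section 7.1 would usually end the trial at the interim. The documents do not support that: 88.8% is the chance of crossing the threshold if d = 0.70 is true, not the chance of stopping. A reader might also treat the power loss and the alpha inflation as one event; the stop that gives 62% is the one that keeps alpha. Nor does 62% describe all the secondaries, since VAE is lower. And 200 patients cannot be called necessary for a sized safety endpoint, because section 9.1 sizes none.

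The gap itself remains. No text confines an efficacy decision to the planned analyses or to 0.025, and no text says whether a positive interim ends enrolment.

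**Conclusion.** The point holds in two conditional parts.

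- **Type I error.** Control of the primary depends on restraint that section 7.1 does not require. Applying the 5% of section 9.2.1 at the two planned looks is enough to take the overall error from 4.3% to 8.3%. Unplanned looks add to it even at 0.025. The size of that addition rests on an assumed number and spacing of looks.
- **Power.** If the trial ends at the section 9.1 interim, the stated 90% for ventilation days and length of stay becomes 62.5%. VAE falls to about 50% on the 20% versus 40% assumption, with the range shown above. Both results assume a stop at exactly 50 per group; at 75 per group, power for d = 0.46 would still be 80%.

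This should be corrected before the interim. It does not show that the trial will stop early or that unplanned looks will occur.

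**What to change.** 1. In section 7.1, take the two efficacy grounds out of open PI discretion. State that efficacy is judged only at the planned interim and the final analysis, each at two-sided 0.025. The safety, compliance, data-quality and futility grounds can stay as they are.
2. In section 9.2.1, exempt the primary endpoint from the general 5% rule.
3. Reconcile the interim timing in sections 3.1 and 9.1.
4. In section 9.1, state whether a positive interim ends enrolment. Either enrolment continues to 200, so that the secondary calculations at 100 per group apply; or early stopping is kept, and the plan states that power after a stop at 50 per group is about 62% for ventilation days and length of stay and lower for VAE (about 50% at 20% versus 40%).

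The cost is protocol wording; the planned 200 does not change. What is given up is the option to stop for efficacy at an arbitrary time. Whether to allow a stop at the planned interim remains the sponsor's choice, provided its consequence is stated.

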7.2. Medical condition resulted in the decision to deliver “Comfort-oriented care”

If during the study patient's medical condition changed and the decision/preferences is NOT to receive aggressive, life-sustaining treatments but to delivered comfort-oriented care (or equivalent according to hospital policy and PI confirmation), subject should be terminated from the study.

If in this case the smART+ feeding tube cannot be removed (since a tube must be kept for drainage purposes and a new tube should not be inserted), the feeding tube can continue to be used for drainage / other treatment purposes under the comfort-oriented care.

Although in this case the smART+ feeding tube can be left inside the patient, it must be disconnected from the smART+ device (and all other smART+ components).

7.3. Follow-Up

No follow-up will be conducted for this study. AE and SAE collection is to be conducted up until the moment the subject study participation is terminated. AEs and SAEs occurring after study termination are not to be collected or reported for the purpose of this study.

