IRB	Institutional Review Board
ISO	International Organization for Standardization
LOS	Length Of Stay

Subject: smART Plus Comparative Study Protocol - Beilinson

ml	milliliter
MOP	Manual of Procedures
NCT	National Clinical Trial
NIH	National Institutes of Health
NIH IC	NIH Institute or Center
NG	Naso-Gastric
PEEP	Positive end expiratory pressure
PI	Principal Investigator
PPI	Proton Pump Inhibitors
QA	Quality Assurance
QC	Quality Control
REE	Resting Energy Expenditure
SAE	Serious Adverse Event
SAP	Statistical Analysis Plan
SOA	Schedule of Activities
SOP	Standard Operating Procedure
VAE	Ventilator Associated Event
APACHE	Acute Physiology and Chronic Health Evaluation

Subject: smART Plus Comparative Study Protocol - Beilinson

1. Protocol Synopsis

Study Title:	Nutrition Monitoring and Feeding Optimization with the smART+ System
Purpose:	To demonstrate the ability of the smART+ System to optimize the delivery of nutrition
Study Design:	Comparative, prospective, stratified randomization
Study Endpoints:	
Primary:
 
Optimization of the delivery of nutrition by the smART+ System as compared to standard of care, by automatically calculating and administering enteral feeding better than standard of care (REE or Calorimeter).
 
Secondary:
 
- Safe use of the entire system (AE/SAE directly related to any of the system components)- Decrease in ICU length of stay from admission to ICU until the decision discharge ordered- Reduction of VAE- Decrease in ventilation days- Decrease in workload related to nurse GRV time- Convenience of use of the system and the user interface (by subjective staff questionnaire)- Assessment of urine flow monitoring related to patient condition and usability
No. of Subjects:	In Beilinson site: 100 patients; 50 patients per group Approximately 200 subjects will be enrolled for the complete multi-center comparative study (100 per group)
Population:	ICU mechanically ventilated patients
Investigational Sites:	Israel, United States, Europe
Principal Investigator:	[name]
Study Duration:	Overall study duration is estimated to enroll for approximately 1 year. Enrollment rate of up to 5 simultaneous patients per site (→ 20 parallel in all 4 sites). Total participation duration: Treatment between 2 days and up to 14 days

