Measured from admission to ICU until the decision to discharge is ordered.

- Reduction of VAE According to the definition from the latest CDC.
- Decrease in ventilation days.

Evaluated by the number of hours of etCO2 from the hospital electronic records

- Decrease in workload related to nurse GRV time.

Patient GRV information obtained through the hospital's electronic records and the usability questionnaires, will be analyzed to determine (a) the estimated nursing time that was expended for GRV activities, and (b) the amounts of GRV removed from the patient.

- Convenience of use of the system and the user interface (by subjective staff questionnaire)

Evaluated via questionnaires filled by physician users and nurse users participating in the study.

- Assessment of urine flow monitoring related to patient condition and usability

Patient lab results obtained through the hospital's electronic records and the usability questionnaires, will be analyzed against smART+ system urine alerts, to determine if the alerts will be useful in diagnosis and usability satisfaction.

 ART MEDICAL PATIENT SAFETY TECHNOLOGY	Number: CRO-C-2822	Date issued: 01-Mar-2021
	Rev.06	Page 16 of 35
Subject: smART Plus Comparative Study Protocol - Beilinson		

3. Study Design

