3.2. End of Study Definition

A participant is considered to have completed the study if he or she has completed all phases of the study including the last scheduled procedure shown in the Schedule of Activities (SoA).

In addition, participant is considered to have completed the study if he/she is no longer required enteral feeding (due to feeding tube removal, medical order, or any other reason which feeding stopped and is not scheduled to be renewed within the 14 days of study duration).

4. Study Population

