- The two-sample T-test or Non-parametric Wilcoxon-Mann-Whitney Rank sum test for independent samples (as is appropriate) will be applied for testing the statistical significance of the difference in the estimated nursing time that was expended for GRV activities, and the amounts of GRV removed from the patient between the study groups.
- Convenience of use of the system and the user interface scores (by subjective staff questionnaire) will be summarized in an appropriate table by study group
- The two-sample T-test or Non-parametric Wilcoxon-Mann-Whitney Rank sum test for independent samples (as is appropriate) will be applied for testing the statistical significance of the difference in the assessment of urine flow monitoring related to patient condition and usability between the study groups.
- The two-sample T-test or Non-parametric Wilcoxon-Mann-Whitney Rank sum test for independent samples (as is appropriate) will be applied for testing the statistical significance of the difference in ICU length of stay (measured from admission to ICU until the decision to discharge is ordered) between the study groups.
- Chi-square test or Fisher's Exact test (as is appropriate) will be applied for testing the statistical significance of the difference in percent of subjects experiencing Ventilation associated events between the study groups.

9.2.5 Safety:

Adverse events will be coded using the Medical Dictionary for Regulatory Activities (MedDRA, most updated version) terminology and presented in tables by System Organ Class (SOC) and Preferred Term (PT).

Subject: smART Plus Comparative Study Protocol - Beilinson

AE data will be listed individually and summarized by SOC and by PT within a system organ class for each study group.

Frequency of TEAEs (Treatment-Emergent Adverse Events) and device-related adverse events will be summarized in tables by SOC, PT and study group and by seriousness.

Chi-square test or Fisher's Exact test (as is appropriate) will be applied for testing the statistical significance of the difference in percent of subjects experienced any AE, drug-related AE and SAE between the study groups.

Concomitant medications entered into the database will be coded using the World Health Organization (WHO) Drug Reference List, which employs the Anatomical Therapeutic Chemical classification system.

10. Regulatory, Ethical, and Study Oversight Considerations

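### ICU length of stay and ventilation days are tested as complete durations, but the plan does not say that either is collected once participation ends

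*Combined protocol and SAP*

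**What the plan says.** - **Endpoints.** Section 2.2 defines ICU length of stay as "Measured from admission to ICU until the decision to discharge is ordered". Ventilation days are the hours of etCO2 found in the hospital's electronic records. Neither definition has a time limit.
- **Participation.** The synopsis (section 1) gives "Treatment between 2 days and up to 14 days". Section 3.2 adds that a "participant is considered to have completed the study if he/she is no longer required enteral feeding". Sections 7.1 and 7.2 end participation at withdrawal and at the move to comfort-oriented care.
- **Follow-up.** Section 7.3: "No follow-up will be conducted for this study". The rest of that section concerns adverse events only.
- **Data collection.** Sections 5.2.8 and 5.3.5 list ICU admission and discharge-order times as chart items in both groups. Breathing data start at ICU admission, with no stated end. The chart items named there are FiO2 and PEEP, whereas the endpoint uses etCO2.
- **Analysis.** Section 9.2.3 applies a two-sample t-test or Wilcoxon-Mann-Whitney test to the "difference in ICU length of stay (measured from admission to ICU until the decision to discharge is ordered) between the study groups", and likewise to ventilation days. There is no rule for patients still in the ICU or still ventilated when participation ends, for early termination, or for death.
- **Sample size.** For each of the two endpoints, section 9.1 claims 90% power with 100 patients per group, taking an "effect size of 0.46" and a t-test at two-sided alpha 0.05.

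**The concern.** A patient may still be ventilated at day 14, or may stop enteral feeding for good while still in the ICU. Participation is then over but the duration is not, and the plan does not say which value enters the test. If section 7.3 is taken to end all data collection, the recorded value is a lower bound that the test treats as the true duration. Sites could read the text differently, so complete and cut durations might be mixed.

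Deaths and comfort-care terminations add a second gap. Both shorten the recorded duration, and a t-test or rank-sum test counts an early death as a short stay.

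These are secondary endpoints, and feeding efficiency is unaffected. They are, however, the endpoints on which section 9.1 rests the final size of 100 per group. The trial is open-label (section 5.1), so the time at which feeding stops may itself differ between groups.

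**Working it through.** **1. The plan's own figure.** Inputs from section 9.1: standardised difference 0.46, two-sided alpha 0.05, power 90%.

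n per group = 2(1.960 + 1.282)² / 0.46² = 2 × 10.51 / 0.2116 ≈ 99.3, so 100. With n = 100, the normal approximation gives Φ(0.46 × √50 − 1.960) = Φ(1.293) = 90.2%; the noncentral t gives 89.9%. The stated figure reproduces. It presumes complete durations.

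**2. What a common cut does to the difference in days.** The documents give no mean, SD or share of patients beyond day 14, so every distribution below is an assumption.

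For an exponential duration with mean m cut at c days, the expected recorded value is m(1 − e^(−c/m)), and a share e^(−c/m) is cut. With c = 14:

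- Means 10 and 6.5: 7.53 − 5.75 = 1.8 days, against a true 3.5 (25% and 12% cut).
- Means 12 and 8: 8.26 − 6.61 = 1.65 days, against a true 4.0 (31% and 17% cut).

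ICU admission may precede enrolment by up to 48 hours (section 4.1), so a participation cut could fall as late as ICU day 16. With c = 16 the two differences are 2.0 and 1.9 days.

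Simulations with 3,000 trials of 100 per group, a true standardised difference of 0.46 and a cut at day 14 gave:

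| Assumed control durations | Difference, complete (days) | Difference, cut (days) | t-test power, complete | t-test power, cut |
|---|---|---|---|---|
| Lognormal, mean 8, CV 0.6 | 1.94 | 1.62 | 90% | 92% |
| Lognormal, mean 12, CV 0.8 | 3.81 | 2.08 | 92% | 96% |
| Lognormal, mean 18, CV 0.6 | 4.39 | 1.38 | 91% | 89% |
| Near-normal, mean 10, SD 5 | 2.18 | 1.83 | 89% | 87% |
| Near-normal, mean 14, SD 7 | 3.11 | 1.77 | 90% | 83% |

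Across all lognormal settings tried (means 8 to 18, CV 0.6 to 1.0), the cut difference was 31% to 83% of the complete one. For near-normal durations it was 57% to 84%.

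**3. Power.** Cutting removes long-tail variance as well as difference, so the direction is not fixed. Lognormal t-test power after the cut was 89–97%, against 90–93% before. Near-normal power fell from 89–90% to 83–87%.

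In the exponential cases, t-test power fell from about 85–86% to 74–76% (means 10 and 6.5) and from 80% to 65% (means 12 and 8). Those cases start from standardised effects below 0.46:

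- 3.5 / √((10² + 6.5²)/2) = 0.415
- 4 / √((12² + 8²)/2) = 0.392

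Part of their shortfall from 90% therefore has nothing to do with the cut. Calibrated to about 0.46, exponential t-test power goes from about 92% to 82–84%. With the rank-sum test the uncalibrated cases move only from about 75% to 72% and from 70% to 66%.

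**4. A cut at feeding stop, with no true effect.** Durations are lognormal with mean 12 and CV 0.8 in both groups. Feeding stops at 2 days plus an exponential time, at most day 14.

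| Mean of the exponential part, control / treated | Apparent benefit (days) | Trials rejecting at 0.05 |
|---|---|---|
| 9 / 9 | 0.01 | 5.1% |
| 9 / 7 | 0.51 | 17.6% |
| 7 / 9 | −0.50 | 17.1% |

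**The case against.** A reader might infer that the plan truncates both endpoints at day 14. The documents do not support that. Fourteen days limits treatment and participation, not the endpoint definitions. Discharge-order time is a required chart item in both groups, which makes most sense if it is read whenever it occurs. The remainder of section 7.3 is about adverse events, so its opening sentence may mean only that there are no follow-up visits or safety follow-up.

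This stands: truncation follows from one plain reading of section 7.3 and is not a stated rule. It does not close the gap, because no section authorises chart collection after participation ends. Ventilation hours are less protected than length of stay, since their data have a start but no end and etCO2 is not named among the chart items. Complete collection would still leave deaths without a rule.

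A reader might also infer that the difference is always understated and that the stated 90% power is lost. That too goes beyond the evidence. The difference in days shrinks under a common day-14 cut, but power holds or rises slightly in most lognormal settings and changes little with the rank-sum test, which section 9.2.3 allows. Withdrawal, comfort care and feeding stop do not cut both groups at the same value, and the last can bias in either direction.

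**Conclusion.** The point holds as an unresolved conflict between the endpoint definitions and the end of participation. Sections 2.2 and 9.2.3 need complete durations; section 7.3, taken literally, does not provide them; and sections 5.2.8 and 5.3.5 do not settle the matter.

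If durations were cut at a common day 14, the difference in days would be understated under every distribution tried with a true effect, to between 31% and 84% of its full value in the lognormal and near-normal settings. No single corrected figure or power can be given, because the plan contains no means, SDs or censoring rates in days. If the cut came at feeding stop and differed by group, a false benefit or a false harm of about half a day could appear, with roughly 17% false rejections under the stopping times assumed. This should be fixed before analysis, although it does not touch the primary endpoint.

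**What to change.** 1. Reconcile section 7.3 with sections 5.2.8 and 5.3.5. State that discharge-order time, end of ventilation (the etCO2 hours) and death are taken from the hospital record for every randomised patient until ICU discharge, whether or not participation has ended. Limit the no-follow-up statement to whatever it is meant to cover.
2. Name etCO2 hours among the chart items in both groups, with a start and an end.
3. In section 9.2.3, state how a death in the ICU enters each comparison.
4. If a cut-off is kept, define one fixed window counted the same way in both groups, with its starting point stated because ICU admission precedes enrolment. Analyse time to event censored at the end of that window, with death as a competing event, and not a t-test on cut values. Feeding stop should not serve as the censoring time.

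The cost is a few chart times per patient after participation ends, with no patient contact, plus wording in the protocol and the statistical section.
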